5.3.6.3. Endpoints Related to Skin Disease

In this study, Other Endpoints for skin disease include those related to CCI

5.3.6.3.1. Related Endpoints

The CCI related Other Endpoints include:

5.3.6.3.3. Method of Analysis

In general, the same methods of analysis for the Other Endpoints related to reduction of signs and symptoms and physical function in Section 5.3.6.2.9 will also be used for those related to skin disease.

Table 9 summarizes the analyses for supportive efficacy endpoints related to skin disease, the methods for analyses, and the data handling rules used.

Table 9: Summary of Estimands, Analysis Sets, Data Handling Rules, and Analysis Methods for Endpoints of Skin Disease

	Endpoint	Analysis Set	Missing Data Rules	Analysis Methods		
	ENDPOINTS BY VISIT THROUGH WEEK 24 AT WEEK-24 DBL, ADJUSTED COMPOSITE ESTIMAND					
1	Proportions of participants with IGA score of 0	FAS with ≥3% BSA and IGA≥2 at baseline	NRI for MAR not due to Natural Disaster or Major Disruption	Summarized descriptively Response rates by intervention group based on GLMM		
2	Proportions of participants with PASI ≥75%, ≥90%, ≥100% improvement	FAS with ≥3% BSA and IGA≥2 at baseline	NRI for MAR not due to Natural Disaster or Major Disruption	Summarized descriptively Response rates by intervention group based on GLMM		
3	Change from baseline in PASI score	FAS with ≥3% BSA and IGA≥2 at baseline	-	 Summarized descriptively LSMeans and 95% CI by intervention group based on MMRM model 		

^{&#}x27;-' indicates no missing data rules to be applied

ENDPOINTS BY VISIT AFTER WEEK 52 THROUGH WEEK 100 AT WEEK-112 DBL, USING ADJUSTED COMPOSITE ESTIMAND

1, 2	Same as through	Same as through	Same as through	 Summarized descriptively Response rates by intervention group
	Week 24	Week 52	Week 52	based on GLMM
3	Same as through Week 24	Same as through Week 52	Same as through Week 52	 Summarized descriptively LSMeans and 95% CI by intervention group based on MMRM model

ENDPOINTS BY VISIT THROUGH WEEK 24 AT WEEK-24 DBL, AFTER WEEK 24 THROUGH WEEK 52 AT WEEK-52 DBL, AND AFTER WEEK 52 THROUGH WEEK 112 AT WEEK-112 DBL

[figure not shown]
USING TREATMENT POLICY ESTIMAND AND THE FAS-UKR ANALYSIS SET INSTEAD OF FAS
The endpoints analyzed using the Adjusted Composite Estimand for corresponding visits/DBL are repeated here,

The endpoints analyzed using the Adjusted Composite Estimand for corresponding visits/DBL are repeated here except:

[figure not shown]
- No imputation will be applied, and all analyses will be based on observed data.
- Continuous endpoints will use ANCOVA instead of MMRM; binary response endpoints will use CMH test
 with CI based on Wald statistics instead of GLMM for visits up to and including Week 24.

5.3.6.4. Endpoints Related to Health-Related Quality of Life and Other Outcomes

In this study, Other Endpoints for HRQOL measures include questionnaires of All Other Endpoints related to CCI **Related Endpoints** 5.3.6.4.1. The related Other Endpoints include:

CONFIDENTIAL – FOIA Exemptions Apply in U.S.

5.3.6.4.5. Method of Analysis

In general, the same methods of analysis for the Other Efficacy endpoints related to reduction of signs and symptoms and physical function in Section 5.3.6.2.9 will also be used for those related to HRQOL.

Table 10 summarizes the analyses for supportive efficacy endpoints related to HRQOL, the methods for analyses, and the data handling rules used.

Table 10: Summary of Estimands, Analysis Sets, Data Handling Rules, and Analysis Methods for Endpoints of HRQOL

	Endpoint	Analysis Set	Missing Data Rules	Analysis Methods
ENDPOI ESTIMA		GH WEEK	24 AT WEEK-24 1	DBL, ADJUSTED COMPOSITE
1	Change from baseline in SF-36 PCS/MCS score	FAS	-	Summarized descriptively LS mean (95% CI) for each intervention group, LS mean difference (95% CI) and p-values for differences between groups based on MMRM
2	Change from baseline in SF-36 domain scales score	FAS	-	Summarized descriptively LS mean (95% CI) for each intervention group, LS mean difference (95% CI) and p-values for differences between groups based on MMRM
3	Change from baseline in PROMIS-29 score	FAS	-	Summarized descriptively LS mean (95% CI) for each intervention group, LS mean difference (95% CI) and p-values for differences between groups based on MMRM
4	Change from baseline in FACIT-F score	FAS	-	Summarized descriptively LS mean (95% CI) for each intervention group, LS mean difference (95% CI) and p-values for differences between groups based on MMRM
5	Proportions of participants with ≥4-point improvement from baseline in FACIT-F score	FAS	NRI for MAR not due to Natural Disaster or Major Disruption	Summarized descriptively Response rates, and treatment difference in response rates and 95% CI and p-value, based on GLMM
6	Change from baseline in PsAID-12 score	FAS	-	Summarized descriptively LS mean (95% CI) for each intervention group, LS mean difference (95% CI) and p-values for differences between groups based on MMRM

^{&#}x27;-' indicates no missing data rules to be applied

ENDPOINTS BY VISIT AFTER WEEK 24 THROUGH WEEK 52 AT WEEK-52 DBL, USING ADJUSTED COMPOSITE ESTIMAND

1, 2, 3, 4, 6	Same as through Week 24	Same as through Week 24	Same as through Week 24	•	Summarized descriptively LSMeans and 95% CI by intervention group based on MMRM model
5	Same as through Week 24	Same as through Week 24	Same as through Week 24	•	Summarized descriptively Response rates by intervention group based on GLMM

ENDPOINTS BY VISIT AFTER WEEK 52 THROUGH WEEK 112 AT WEEK-112 DBL, USING ADJUSTED COMPOSITE ESTIMAND

	Endpoint	Analysis Set	Missing Data Rules	Analysis Methods
1, 2, 3, 4, 6	Same as through Week 24	Same as through Week 24	Same as through Week 24	 Summarized descriptively LSMeans and 95% CI by intervention group based on MMRM model
5	Same as through Week 24	Same as through Week 24	NRI for MAR not due to Natural Disaster or Major Disruption	 Summarized descriptively Response rates by intervention group based on GLMM

Table 10: Summary of Estimands, Analysis Sets, Data Handling Rules, and Analysis Methods for Endpoints of HRQOL

ENDPOINTS BY VISIT THROUGH WEEK 24 AT WEEK-24 DBL,
AFTER WEEK 24 THROUGH WEEK 52 AT WEEK-52 DBL, AND
AFTER WEEK 52 THROUGH WEEK 112 AT WEEK-112 DBL
USING TREATMENT POLICY ESTIMAND AND THE FAS-UKR ANALYSIS INSTEAD OF FAS

The endpoints analyzed using the Adjusted Composite Estimand for corresponding visits/DBL are repeated here, except:

- No imputation will be applied, and all analyses will be based on observed data.
- Continuous endpoints will use ANCOVA instead of MMRM; binary response endpoints will use CMH test with CI based on Wald statistics instead of GLMM for visits up to and including Week 24.

5.4. Safety Analyses

All safety analyses will be based on the safety analysis set based on **actual** intervention received. Safety will be assessed by summarizing the occurrences and type of AEs, vital signs (pulse, blood pressure, and weight) and examining the changes in the laboratory parameters. No formal statistical comparison is planned.

5.4.1. Safety Tables Presentation

There are 3 DBLs in this study, respectively, at Week 24, Week 52, and End of Study (Week 112). Depending on the safety data categories, the cumulative safety data will be analyzed through different study periods which include, but are not limited to, through Week 24 and through end of study periods. Tabular summaries of safety events for key study periods are in general presented as follows:

5.4.1.1. Summaries Through Week 24

Safety data through Week 24 will be analyzed according to the following intervention groups:

- 1. **Placebo**: Participants who received placebo only and no guselkumab prior to Week 24.
- 2. **Guselkumab 100 mg at Weeks 0, 4, and then q8w**: Participants who received guselkumab 100 mg q8w prior to Week 24 with an additional dose at Week 4.
- 3. **Guselkumab 100 mg q4w**: Participants who received guselkumab 100 mg q4w prior to Week 24.
- 4. **Guselkumab Combined:** Participants in Groups 2 and 3.

The above intervention groups 1-3 are **mutually exclusive**. This allows between-group comparisons of safety between a guselkumab group and the placebo group based on similar follow-up period in each group. The safety tables will have the column headings below:

		Guselkumab		
	Placebo	100 mg q8w	100 mg q4w	Combined
Analysis set: Safety Analysis Set	###	###	###	###

For participants who started treatment with placebo only but later received any amount of guselkumab prior to Week 24 inadvertently, the safety events/measurements on and after the first dose of guselkumab, will be excluded from the data summaries through Week 24. Only the safety events/measurements that occurred while the participants had been receiving placebo only will be included in the data summaries through Week 24.

5.4.1.2. Summaries Through Week 52

Safety data through Week 52 will be analyzed according to the following intervention groups:

- 1. **Placebo:** Participants who received placebo only. Follow-up will be based on the period that the participant was on placebo from the first dose up to Week 52.
 - a. For participants who started treatment with placebo and later received treatment with guselkumab (due to CO or inadvertently), follow-up will end at the first dose of guselkumab, and only the safety events/measurements that occurred prior to the first dose of guselkumab will be included in this group.
- 2. Placebo → Guselkumab 100 mg q4w: Participants who started treatment with placebo and later received treatment with guselkumab (due to CO or inadvertently). Follow-up will start from the first dose of guselkumab up to end of study. All the safety events/measurements that occurred on and after the first dose of guselkumab up to end of study will be included in this group.
- 3. **Guselkumab 100 mg at Weeks 0, 4, and then q8w**: Participants who received guselkumab 100 mg q8w prior to Week 24 with an additional dose at Week 4. Follow-up will be from the first dose up to Week 52.
- 4. **Guselkumab 100 mg q4w**: Participants who received guselkumab 100 mg q4w prior to Week 24. Follow-up will be from the first dose up to end of study.
- 5. **Guselkumab 100 mg q4w Combined:** Participants in Groups 2 and 4.
- 6. All Guselkumab Combined: Participants in Groups 2, 3, and 4.

The above intervention groups 1-2 are **not mutually exclusive**. The safety tables will have the column headings below:

	Guselkumab					
		Placebo				
	\rightarrow 100			100 mg q4w	All	
	Placebo	100 mg q4w	100 mg q8w	100 mg q4w	Combined	Combined
Analysis set: Safety Analysis Set	###	###	###	###	###	###

CONFIDENTIAL – FOIA Exemptions Apply in U.S.

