4.5. Safety Analysis Set

All participants who received at least one (complete or partial) administration of any study intervention, ie, the treated population. This analysis set will be used for the safety analyses.

In the analyses for this set, participants will be analyzed per the study intervention they **actually received**, regardless of the study intervention they were randomized to.

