5.4.3. Adverse Events

The verbatim terms used in the eCRF by investigators to identify AEs will be coded using the Medical Dictionary for Regulatory Activities (MedDRA). Any AE occurring at or after the initial administration of study intervention and those AEs that were present at baseline but worsened in severity after the start of initial study intervention are considered to be treatment emergent. If the event occurs on the day of the initial administration of study intervention, and either event time or time of administration are missing, then the event will be assumed to be treatment emergent. If the event date is recorded as partial or completely missing, then the event will be considered to be treatment emergent unless it is known to be prior to the first administration of study intervention based on partial onset date or resolution date. All reported treatment-emergent adverse events will be included in the analysis. For each adverse event, the number and percentage of participants who experience at least 1 occurrence of the given event will be summarized by intervention group.

Summary tables will be provided for treatment-emergent adverse events:

- Treatment emergent adverse events (TEAEs)
- Treatment emergent SAEs
- TEAEs with severe intensity
- TEAEs leading to permanent discontinuation of study intervention
- TEAEs reasonably related to study intervention
- SAEs reasonably related to study intervention

- TEAEs leading to dose interruption of study intervention
- Treatment emergent infections
- Treatment emergent serious infections
- Treatment emergent infections requiring oral or parenteral anti-microbial treatment
- Injection-site reactions
- Venous thromboembolism (VTE) events
- Clinically important hepatic disorder events
- Anaphylaxis, hypersensitivity and serum sickness reactions
- TEAEs leading to death

All AE summary tables will include average weeks of follow-up and average number of study intervention for each intervention group.

In addition to the summary tables, listings will be provided for participants who had:

- SAEs
- TEAEs leading to permanent discontinuation of study intervention
- Anaphylactic reactions or serum sickness reactions
- Malignancies
- Serious infections including TB
- TEAEs leading to death
- Venous thromboembolism (VTE) events
- Major adverse cardiovascular events (MACE) events
- Clinically important hepatic disorder events
- Opportunistic infections

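### The through-Week-24 safety tables have no column for events in placebo participants after an inadvertent guselkumab dose, so the Week 24 report defers these events and under-reports them

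*SAP*

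**What the plan says.** SAP 5.4.1.1 defines four columns for safety through Week 24.

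- **Placebo:** "Participants who received placebo only and no guselkumab prior to Week 24".
- **q8w and q4w:** participants who received those regimens before Week 24.
- **Combined:** "Participants in Groups 2 and 3", that is, q8w plus q4w.

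The first three groups are declared mutually exclusive, and the reason given is: "This allows between-group comparisons of safety between a guselkumab group and the placebo group based on similar follow-up period in each group".

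For a participant who starts on placebo and receives any guselkumab by mistake before Week 24, "the safety events/measurements on and after the first dose of guselkumab, will be excluded from the data summaries through Week 24". The section then adds: "Only the safety events/measurements that occurred while the participants had been receiving placebo only will be included in the data summaries through Week 24".

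Three other parts of the SAP bear on the same events:

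- Section 4.5 says that in the safety analysis set "participants will be analyzed per the study intervention they" actually received. Section 5.4 repeats this for all safety analyses.
- Section 5.4.3 says: "All reported treatment-emergent adverse events will be included in the analysis".
- Section 5.4.1.2 (through Week 52) has a Placebo → Guselkumab q4w group, described as "Participants who started treatment with placebo and later received treatment with guselkumab (due to CO or inadvertently". Events from the first guselkumab dose onward go there. Section 5.4.1.3 carries the rule to the end of the study.

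**The concern.** An adverse event after a real guselkumab injection is what a safety table by actual treatment is meant to show. Under 5.4.1.1, such an event in a placebo participant before Week 24 has no cell in any column. The Week 52 tables count it, so the two reports will not reconcile and nothing in the SAP explains the difference.

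The Week 24 tables matter because they are the only ones confined to the placebo-controlled period with comparable follow-up across arms. Results from the Week 24 lock are also the first to be disclosed (Protocol 10.5.7).

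The rule is incomplete as well. The affected participant does not meet the Placebo definition, which requires no guselkumab before Week 24, yet the pre-dose events are kept. Section 5.4.1.1 does not say which column or denominator they belong to, or when follow-up stops. Section 5.4.2 refers to 5.4.1 for follow-up duration, and 5.4.3 puts average follow-up in every adverse event table, so the number has to be derived from something.

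**Working it through.** No stated sample size, power or alpha is at issue, so there is no plan figure to reproduce. The check is mainly a comparison of text.

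**Where a post-dose event can go**

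Take a placebo participant given guselkumab in error at Week 12, with a non-serious infection at Week 14.

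| Output | Placebo | q8w | q4w | Combined guselkumab | Separate switch column |
|---|---|---|---|---|---|
| Through Week 24 (5.4.1.1) | excluded by rule | not on this regimen | not on this regimen | q8w + q4w only, so no | none exists |
| Through Week 52 (5.4.1.2) | ends at first guselkumab dose | no | no | yes (q4w Combined, All Combined) | yes |
| End of study (5.4.1.3) | as Week 52 | no | no | yes | yes |

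**What the listings still show**

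The exclusion names data summaries, and 5.4.3 plans listings in addition to the tables. The adverse event listings cover:

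- serious events, deaths and events leading to permanent discontinuation;
- anaphylactic and serum sickness reactions;
- malignancies, serious and opportunistic infections;
- VTE, MACE and clinically important hepatic events.

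Section 5.4.4.1 lists laboratory values of Grade 3 or higher and liver tests above stated thresholds. Non-serious events that do not lead to discontinuation, including injection-site reactions and non-serious infections, would have no Week 24 table and generally no planned adverse event listing.

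**Scale**

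The documents give 150 participants per group, hence 300 on guselkumab through Week 24, and six placebo injections before crossover (Weeks 0, 4, 8, 12, 16, 20). They give no dispensing-error rate.

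Assume an error probability *e* per injection. The expected number of placebo participants with at least one guselkumab dose is 150 × (1 − (1 − e)^6):

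- e = 0.1%: 0.9
- e = 0.2%: 1.8
- e = 0.5%: 4.4

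Now assume *k* affected participants and, as a worst case, that each has the event in question. The change in a pooled guselkumab percentage if they were counted is (r + k)/(300 + k) − r/300, where r is the number of events already in Combined.

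| k (assumed) | From r = 0 | From r = 150 (50%) | Share of exposed participants omitted, k/(300 + k) |
|---|---|---|---|
| 1 | +0.33 points | +0.17 points | 0.33% |
| 3 | +0.99 | +0.50 | 0.99% |
| 5 | +1.64 | +0.82 | 1.64% |
| 10 | +3.23 | +1.61 | 3.23% |

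For a rare event the expected loss is small. With 0.9 to 4.4 affected participants and an assumed 1% risk each, it is 0.9 × 0.01 = 0.009 to 4.4 × 0.01 = 0.044 events.

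**The case against.** The best defence is that the rule protects a clean comparison. A placebo participant with a stray guselkumab dose is no longer placebo-only and has received neither regimen. Attributing later events to Placebo would contaminate it, and adding them to Combined would bring in late-starting, partial exposure. Kits are assigned through the IWRS, dosing before Week 24 is by or under the supervision of site staff, and no formal safety comparison is planned. All of this stands. It justifies keeping the events out of Placebo, q8w, q4w and Combined. It does not justify leaving them out of the Week 24 output altogether, and it does not settle the denominator or the follow-up cut-off.

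A reader might infer several stronger things that the documents do not support:

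- **That the harms are lost.** Sections 5.4.1.2 and 5.4.1.3 name inadvertent recipients and count their events, and serious events are in the listings.
- **That this is the only placebo-controlled safety summary.** The Week 52 and end-of-study tables also carry a Placebo column, although with shorter follow-up than the guselkumab columns.
- **That the rule is one-sided because no mirror rule exists for guselkumab participants.** A guselkumab participant given a wrong syringe remains exposed to guselkumab and stays in a guselkumab column, so no mirror rule is needed.
- **That the events belong in Combined.** That would break the identity Combined = q8w + q4w and the similar-follow-up purpose. It is a trade-off, not a correction.

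**Conclusion.** The point holds as a reporting gap in the Week 24 output. Section 5.4.1.1 excludes these events, no Week 24 column can take them, and the exclusion sits badly with 4.5, 5.4 and 5.4.3 and differs from 5.4.1.2. Section 5.4.1.1 can be read as a specific presentation rule that overrides the general statements, but the SAP does not say so.

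The likely size is small. The number affected is unknown, and the figures of about 1 to 4 participants rest wholly on assumed error rates. At 300 guselkumab participants, each omitted participant changes a pooled percentage by at most about 0.33 points. No test or efficacy conclusion is touched. The practical consequence is that non-serious post-exposure events, and the table count of any rare serious one, would be missing from the Week 24 report until the Week 52 lock. The change is worth making because it is cheap, not because the safety conclusions are in doubt.

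**What to change.** In SAP 5.4.1.1:

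1. Keep Placebo, q8w, q4w and Combined as the comparison columns.
2. State that a placebo participant who inadvertently receives guselkumab before Week 24 stays in the Placebo column and denominator, with follow-up ending at the first guselkumab dose, as 5.4.1.2 already does. Adjust the wording of the Placebo definition to match.
3. Report all events and measurements from that dose through Week 24 in a separate *Placebo → Guselkumab (inadvertent)* column, or in a footnote plus a listing, giving the number of participants and events.
4. Add a cross-reference saying that the same events enter the Placebo → Guselkumab q4w and combined columns from Week 52, so that the reports can be reconciled.

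The cost is a few sentences and a flag that the Week 52 tables need anyway. The downside is one extra column or footnote that will usually be near-empty.

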- d. If a participant discontinues study drug intervention prior to the Week 24 visit, they should be encouraged to return for all remaining study visits through Week 24. The participant should also return for a final safety visit to perform assessments under the Week 112/final safety visit approximately 12 weeks after the last study intervention administration. If a participant permanently discontinues study intervention administration at or after the Week 24 and before the Week 100 visit, the final efficacy visit should occur at the time of discontinuation or as soon as possible and all assessments under the Week 100/final efficacy visit should be performed. Fasting is not required for the final efficacy visit. The participant should also return for a final safety visit to perform assessments under the Week 112/final safety visit approximately 12 weeks after the last study intervention administration.
- e. Must be signed before first study-related activity.
- f. Participants with spondylitis with peripheral arthritis as their primary arthritic presentation of PsA will have confirmation of sacroilitis during screening by a centrally read pelvic X-ray (ie, anteroposterior views of the sacrum). An existing X-ray done within 3 months of screening may be sent for central reading in lieu

- of a screening X-ray (and if not of sufficient quality, a new screening X-ray would then be performed and centrally read). Participants who have confirmed sacroiliitis will complete the BASDAI at specified visits in the SoA.
- g. Study intervention will be administered SC q4w by a healthcare professional during visits to the site until the participant (or caregiver) is trained for self-administration. Study intervention will be administered by site personnel at Weeks 0 and 4. Beginning at Week 8, at the discretion of the investigator and participant, and after appropriate and documented training, participants (or caregiver) may administer study intervention at the investigative site under the supervision of a health care professional. After appropriate training, beginning at Week 32, participants (or caregiver) may administer study intervention at home and on-site visits are only required at Weeks 36, 44, and 52. Safety and efficacy assessments, including blood samples for clinical laboratory and pharmacokinetics/immunogenicity, as specified in the SoA should be performed prior to study intervention administration.

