5.4.4. Additional Safety Assessments

5.4.4.1. Clinical Laboratory Tests

Clinical laboratory tests will be displayed for the participants included in the safety analysis set.

The clinical laboratory parameters to be evaluated by the central laboratory include but are not limited to:

• Hematology: basophils, eosinophils, hemoglobin, hematocrit, lymphocytes, monocytes, neutrophils, platelets, red blood cell (RBC) count and white blood cell (WBC) count

• Clinical chemistry: albumin, alkaline phosphatase, alanine aminotransferase (serum glutamate pyruvate transaminase) [ALT (SGPT)], aspartate aminotransferase (serum glutamic oxaloacetic transaminase) [AST (SGOT)], bicarbonate, blood urea nitrogen (BUN), calcium, chloride, creatinine, glucose, potassium, sodium, total bilirubin, and total protein

Due to the Major Disruption resulting from the conflict involving Ukraine and neighboring countries/territories beginning 24 February 2022, central labs were unavailable for some sites over a period of time. In these instances, local labs, limited to the following parameters, may have been entered into the eCRFs: sodium, potassium, chloride, bicarbonate, BUN, creatinine, total bilirubin, direct bilirubin (conditionally), indirect bilirubin (conditionally), AST, ALT, gamma-glutamyltransferase (GGT), alkaline phosphatase (ALP), and LDH. Certain analyses will use central lab data only, while other analyses may use a combination of central lab data and local lab data.

Descriptive statistics and graphical displays of observed values and changes from baseline will be presented for selected chemistry and hematology laboratory tests at scheduled time points. Only central lab data will be used for this analysis.

Shift tables from baseline to post-baseline will be produced for select laboratory parameters. Both central and local lab data will be used for this analysis.

Abnormality criteria based on toxicity grade will be applied to baseline and post-baseline values using National Cancer Institute's Common Terminology Criteria for Adverse Events (NCI-CTCAE) for parameters with NCI-CTCAE criteria defined (Appendix 9). Applicable laboratory results will be graded according to NCI-CTCAE version 5.0. Both central and local lab data will be used for this analysis. Abnormality for selected chemistry and hematology laboratory tests will be summarized by study intervention for:

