- Number and percent of participants with post-baseline values by maximum toxicity grade
- Listings of participants with any post-baseline lab value of NCI-CTCAE toxicity Grade 3 or higher

Number and percent of participants with post-baseline elevated liver chemistry tests will also be produced using both central and local lab data, for:

ALT categories

- >1x to <3x Upper limit of normal (ULN)
- $>3 \times \text{ to } <5 \times \text{ULN}$
- $>5 \times \text{ to } < 8 \times \text{ULN}$
- ≥8×ULN

AST categories

- $>1 \times \text{to} < 3 \times \text{ULN}$
- $>3 \times \text{ to } <5 \times \text{ULN}$

- \geq 5× to <8×ULN
- >8×ULN

Total Bilirubin categories:

- $>1 \times \text{to} < 2 \times \text{ULN}$
- ≥2×ULN

ALP categories:

- $>1 \times$ to $<2 \times$ ULN
- $>2\times$ to $<4\times$ ULN
- ≥4×ULN

Both central and local lab data will be used for this analysis.

Number and percent of participants who met each of the following 5 liver function biochemical criteria individually, as well as overall (ie, met any of the 5), as determined by the investigator, will be summarized:

• ALT or AST absolute:

ALT or AST ≥8×ULN

• ALT or AST increase:

ALT or AST \geq 5×ULN but <8×ULN persists for \geq 2 weeks, OR

ALT or AST $\ge 3 \times ULN$ but $< 5 \times ULN$ persists for ≥ 4 weeks

• ALT/AST/Bilirubin or ALT/AST/INR:

ALT or AST $\geq 3 \times ULN$ and total bilirubin $\geq 2 \times ULN$, OR

ALT or AST ≥3×ULN and INR >1.5

• Cannot monitor:

ALT or AST \geq 5×ULN but \leq 8×ULN and cannot be monitored weekly for \geq 2 weeks, OR

ALT or AST $\ge 3 \times ULN$ but $< 5 \times ULN$ and cannot be monitored weekly for ≥ 4 weeks

• Symptomatic:

ALT or AST $\ge 3 \times ULN$ associated with symptoms (new or worsening) believed to be related to liver injury or hypersensitivity

Listings of participants meeting ANY biochemical criteria of post-baseline ALT≥3x ULN, AST≥3x ULN, ALP≥2x ULN, OR total bilirubin≥2x ULN will be created. Additionally, participants will be assessed for the following 2 Combined Biochemical Criteria:

- 1) Total bilirubin $\ge 2xULN$ within 5 days after either ALT or AST $\ge 3xULN$.
- 2) INR >1.5 within 5 days after either ALT or AST $\geq 3xULN$.

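### The Placebo→q4w safety column has no baseline reset and no new-or-worsened condition, so laboratory and vital-sign abnormalities that began on placebo and persist are tabulated as q4w findings

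*SAP*

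**What the plan says.** SAP 5.4.1.2 allocates safety data by time of measurement. For a placebo participant who later receives guselkumab, the Placebo column stops at that dose: "only the safety events/measurements that occurred prior to the first dose of guselkumab will be included in this group". In the Placebo→q4w column, all safety "events/measurements that occurred on and after the first dose of guselkumab up to end of study will be included in this group". The q4w Combined column is defined as "Participants in Groups 2 and 4", so it takes in the crossover data, and All Guselkumab Combined adds q8w. SAP 5.4.1.3 carries the same scheme to end of study.

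The summaries that fill these columns depend on a baseline or on being after one. In SAP 5.4.4.1, "Descriptive statistics and graphical displays of observed values and changes from baseline will be presented" for selected tests, and "Shift tables from baseline to post-baseline will be produced for select laboratory parameters". For toxicity, "Abnormality criteria based on toxicity grade will be applied to baseline and post-baseline values", and the reported quantity is "Number and percent of participants with post-baseline values by maximum toxicity grade". SAP 5.4.4.2 summarises vital-sign change from baseline, and Table 11 combines an absolute limit with a change from baseline. In SAP Appendix 9, the grades for ALT, AST, alkaline phosphatase, bilirubin and GGT depend on whether baseline was normal.

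Neither document says which baseline applies to the Placebo→q4w column. Protocol 6.4 identifies Week 0 as the baseline visit. The one safety baseline the SAP defines outright, for the eC-SSRS (5.4.4.4.1), uses screening and Week 0.

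**The concern.** A time window works for adverse events, which have an onset date. It works less well for measurements repeated at every visit. Hematology and chemistry are drawn at Weeks 20, 24 and 28 (Protocol 1.3), so one stable abnormality can appear on both sides of the crossover. It is then counted under Placebo and again under q4w, although nothing changed on drug.

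The crossover is meant to add safety data on q4w (Protocol 4.1), and Protocol 2.2.1.1.3 reports slightly more transaminase increases with q4w than with q8w in the earlier studies. Early escape at Week 16 allows placebo participants to start or increase methotrexate or leflunomide (Protocol 6.8.1, Table 4), which is one plausible source of laboratory changes shortly before crossover. A reader of the Placebo→q4w or q4w Combined column would take its counts as findings on q4w.

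**Working it through.** The documents give no figure on this point, so there is none to reproduce. The check applies the SAP's own rules to worked cases and then bounds the dilution. The cases are assumed values, not trial data.

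**1. ALT grade (SAP Appendix 9).** With a normal baseline, grades use multiples of ULN: Grade 1 above 1 to 3, Grade 2 above 3 to 5, Grade 3 above 5 to 20. With a baseline above ULN, they use multiples of baseline: Grade 1 from 1.5 to 3, Grade 2 above 3 to 5. Week 0 ALT is taken as 0.8×ULN.

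| Last value before guselkumab (×ULN) | Value after (×ULN) | Grade, Week 0 baseline | Ratio to last pre-guselkumab value | Grade, reset baseline |
|---|---|---|---|---|
| 2 | 2 | 1 | 1.0 | 0 |
| 3.5 | 3.5 | 2 | 1.0 | 0 |
| 6 | 6 | 3 | 1.0 | 0 |
| 2 | 7 | 3 | 7/2 = 3.5 | 2 |

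The first three rows show no change on drug, yet score Grade 1 to 3 under q4w. The last row is a real worsening, and the reset still captures it.

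**2. Pulse (SAP Table 11: above 120 bpm and up by more than 30 bpm).** Pulse is 80 at Week 0, 122 at Week 24 and 122 at Week 28. Against Week 0 the change is 122 − 80 = +42, so it is markedly abnormal. Against Week 24 it is 122 − 122 = 0, so it is not.

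**3. Where a reset alone does nothing.** The liver categories in SAP 5.4.4.1 are multiples of ULN, and CTCAE terms such as hemoglobin, neutrophils and platelets have absolute cut-offs. ALT of 3.5×ULN at Week 28 falls in the 3 to 5×ULN category whatever the baseline. Attribution here comes from the window rule, so only a new-or-worsened condition changes it.

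**4. Dilution.** Let *f* be the share of crossover participants who carry an abnormality across the first guselkumab dose and have no new or worse value on drug. The documents give no such rate, so *f* is assumed at 1% to 10%. With the planned 150 per group (SAP 1.2), q4w Combined has 150 + 150 = 300 and All Guselkumab Combined has 450. Points added = 100 × 150*f* / N.

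| *f* | Participants | Placebo→q4w (150) | q4w Combined (300) | All Combined (450) |
|---|---|---|---|---|
| 1% | 1.5 | 1.0 | 0.5 | 0.3 |
| 2% | 3 | 2.0 | 1.0 | 0.7 |
| 5% | 7.5 | 5.0 | 2.5 | 1.7 |
| 10% | 15 | 10.0 | 5.0 | 3.3 |

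**5. Week 24 sample.** Protocol 1.3, footnote g, requires that assessments "as specified in the SoA should be performed prior to study intervention administration". The crossover dose is given at the same visit, so the Week 24 value precedes it. Under the Placebo column's wording it belongs to placebo.

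**The case against.** The strongest objection concerns direction. A reader might infer that the carry-over inflates q4w relative to q8w, but the documents do not support that. The q8w column runs from first dose to Week 52 and counts background abnormalities arising in Weeks 0 to 24. The Placebo→q4w column starts at about Week 24. With a common Week 0 baseline, the same background in every arm and no drug effect, the chance of an abnormality in Weeks 24 to 52 cannot exceed the chance in Weeks 0 to 52. More early escape on placebo could weaken this argument, but nothing in the documents quantifies it. The objection stands, and it also rules out a new-or-worsened condition applied to the crossover column alone: that would strip background from part of q4w Combined and none of q8w.

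Two other readings also go too far. That Week 0 is deliberately retained is inferred from silence: the SAP defines no laboratory or vital-sign baseline. That the Week 24 sample falls under q4w requires applying the window by date. The SAP does not say to do so, and for events on the day of first dosing SAP 5.4.3 refers to times.

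It is also fair that SAP 5.4.1.2 declares the Placebo and Placebo→q4w groups not mutually exclusive, that the randomised q4w column contains no crossover data, that SAP 5.4 plans no formal comparison, and that listings identify participants with Grade 3 or higher values or raised liver tests. These limit the consequence. They do not tell a reader which counts in the crossover and combined columns began on placebo.

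**Conclusion.** The point holds as a gap in the SAP. The window rule, with no reset and no new-or-worsened condition, places abnormalities that arose on placebo and persist or recur after the first guselkumab dose in Placebo→q4w, q4w Combined and All Guselkumab Combined. This rests on Week 0 being the baseline, which is the default reading because it is the only baseline visit identified. For categories defined by ULN multiples or absolute cut-offs it follows from the window rule alone. Abnormalities that resolve before crossover and do not recur stay in the Placebo column.

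The size is unknown. The 0.5 to 5.0 points for q4w Combined assume 1% to 10% carry-over and that all 150 planned placebo participants cross over. No bias against q4w relative to q8w is shown. The through-Week-24 tables are not affected. The change is worth making because it is cheap and bears on the tables meant to extend the q4w safety record.

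**What to change.** Amend SAP 5.4.1.2 (with 5.4.1.3 following), 5.4.4.1, 5.4.4.2 and Appendix 9:

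- For Placebo→q4w, and its contribution to both combined columns, define baseline as the last value before the first guselkumab dose. Use it for change from baseline, shift tables, baseline-dependent CTCAE grades and Table 11. Keep Week 0 for the randomised columns, so that each guselkumab column is measured from its own pre-treatment value.
- For maximum toxicity grade and the ULN-multiple liver categories, present values that are new or worsened from the column's own pre-treatment baseline, by the same rule in every column.
- State that the Week 24 sample taken before the crossover dose belongs to the placebo period.

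The cost is SAP wording, one derived baseline flag and a table footnote explaining the two baselines. By-visit changes in the Placebo→q4w column would no longer be measured from Week 0.
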